3.3.12 CCI [Redacted]

[Redacted]

[Redacted]

[Redacted]

[Redacted]

[Redacted]

[Redacted]

[Redacted]

[Redacted]

[Redacted]

CCI [REDACTED]

[REDACTED]

[REDACTED]

[REDACTED]	[REDACTED]	
	[REDACTED]	[REDACTED]
	[REDACTED]	[REDACTED]
	[REDACTED]	[REDACTED]
	[REDACTED]	[REDACTED]
	[REDACTED]	[REDACTED]
	[REDACTED]	[REDACTED]
	[REDACTED]	[REDACTED]
[REDACTED]	[REDACTED]	
	[REDACTED]	[REDACTED]
	[REDACTED]	[REDACTED]
	[REDACTED]	
	[REDACTED]	[REDACTED]
	[REDACTED]	[REDACTED]
[REDACTED]	[REDACTED]	

3.3.13 CCI [REDACTED]

[REDACTED]

3.3.14 SLEDAI-2K

The effect of anifrolumab compared with placebo on SLEDAI-2K score will be evaluated using the difference in mean change from baseline to Week 52 and to Week 104.

The SLEDAI-2K assessment (see Appendix F in the clinical study protocol) consists of 24 lupus-related items. It is a weighted instrument, in which descriptors are multiplied by a particular organ's "weight" and then these are totalled into the final score. The SLEDAI-2K score range is 0 to 105 points with 0 indicating inactive disease. The SLEDAI-2K will be calculated using a timeframe of 30 days in this study.

3.3.15 Non-renal SLEDAI-2K

Extra-renal disease activity will be assessed by using the SLEDAI-2K score (as defined in Appendix E in the clinical study protocol) without the renal components ("non-renal SLEDAI-2K"). The renal components that will not be included for this assessment are proteinuria, hematuria, pyuria and urinary casts. The score range for the non-renal SLEDAI-2K is therefore 0 to 89 with 0 indicating inactive disease. The effect of anifrolumab compared with placebo on non-renal SLEDAI-2K will be evaluated using the difference in mean change from baseline to Week 52 and Week 104.

3.3.16 Physician Global Assessment

The effect of anifrolumab compared with placebo on PGA will be evaluated using the difference in mean change in PGA from baseline to Week 52 and to Week 104.

PGA is a visual analogue scale (VAS) measuring the physician's overall assessment of average disease severity over the last 4 weeks and ranges from 0 (none) to 3 (severe).

PGA may be completed after the visit, to allow for laboratory results, as long as this is done prior to the next scheduled visit. Therefore, the date of the associated scheduled visit (Week 0 etc.) will be used to determine baseline (and subsequent visits), and not the actual date of the assessment.

3.3.17 SLICC/ACR Damage Index

The endpoint used to evaluate the effect of anifrolumab compared with placebo on irreversible damage in SLE subjects is the mean change in SDI global score (as defined in Appendix M in the clinical study protocol) from baseline to Week 52 and to Week 104. SDI will be listed by organ system.

The SDI is defined for 12 organ systems (possible scores): peripheral vascular (0 to 5), ocular (0 to 2), neuropsychiatric (0 to 6), renal (0 to 3), pulmonary (0 to 5), cardiovascular (0 to 6), gastrointestinal (0 to 6), musculoskeletal (0 to 7), skin (0 to 3), endocrine (diabetes) (0 to 1), gonadal (0 to 1) and malignancies (0 to 2). The SDI global score is the sum of the damage scores for all 12 organ systems. Damage over time can be stable or increase (but not decrease from the baseline value), theoretically to a maximum of 47 points.

3.4 Subject reported outcome variables

3.4.1 Patient Global Assessment

The difference between anifrolumab and placebo in the mean change from baseline in PtGA to Week 52 and to Week 104 will be assessed.

PtGA is a VAS completed by subjects asking a single-item question “Considering all the ways in which illness and health conditions may affect you at this time, please make a mark below to show how you are doing”. The VAS measures from 0 mm (Very Well) to 100 mm (Very Poorly).

3.5 Assessment of study population

3.5.1 Demographic and baseline characteristic variables

Demographic characteristics (including geographic region [Asia Pacific: Australia, Republic of Korea, Taiwan; Europe: Belgium, France, Germany, Hungary, Italy, Poland, Russian Federation, Serbia, Spain, South Africa, United Kingdom; Latin America: Argentina, Mexico, Peru; North America: United States], age, sex, ethnicity and race) and baseline characteristics (including height, weight, body mass index [BMI] and disease characteristics [including SLEDAI-2K, PGA, SLICC/ACR, OCS use, OCS dose, time from LN diagnosis to randomisation, 4-gene type I IFN status, antinuclear antibody [ANA], anti-dsDNA, C3, C4, 24-hour UPCr, spot UPCr, eGFR, inactive urine sediment and MMF dose at randomisation]) will be assessed.

3.5.2 Stratification factors at randomisation

Stratification factors are:

- Results of IFN test at screening using a 4-gene type I IFN test (high versus low)
- 24-hour UPCr ≤ 3.0 mg/mg versus >3.0 mg/mg (based on 24-hour UPCr performed on a sample obtained within 14 days prior to the expected date of randomisation). Without the results of the second (stratification) sample, subjects cannot be randomised. Turn-around time for results from central laboratory is up to 7 days.

On rare occasion an extension of 30-day screening window may be allowed if the re-collection of the 24-hour UPCr or other required samples is necessary or if the results needed for randomisation are delayed. The number of subjects in each strata will be summarised.

3.5.3 Surgical and medical history

Surgical and medical histories will be coded using the latest version of the Medical Dictionary for Regulatory Activities (MedDRA). Medical history will be evaluated separately for past and current conditions as given in the electronic case report form (eCRF).

3.5.4 Prior and concomitant medications

All medications will be coded using the latest version of the WHO Drug Dictionary.

Any medications taken by the subject prior to the first dose date of IP will be considered prior medication. Any medication taken by the subject at any time between the date of the first dose (including the date of the first dose) of IP up to Week 104, inclusive, will be considered concomitant medication. Any medication that started prior to the first dose of IP and ended after the first dose up to Week 104 or is ongoing will be considered as both prior and

concomitant medication. Medications that start during the follow-up period will only be displayed in listings.

In the case that the end date of a concomitant medication (including sponsor provided MMF) is the same as the start date of another record of the same ATC code and same administration route, the end date of the record with the earlier start date will be considered to be one day earlier than the recorded end date, to avoid double counting of medication use in one day. If a medication cannot be classified as prior or concomitant due to missing or partial dates, the imputation rules as given in [Appendix D](#) will be applied.

3.5.5 Exposure of IP

The duration of exposure to the IP per subject is defined as the number of days between the start and the end dates of IP plus the dosing frequency time:

$$\text{Duration of exposure (days)} = (\text{Last dosing date} + 28 \text{ days}) - \text{first dosing date} + 1.$$

The total number of infusions will be counted per subject. Furthermore, the number of subjects with an infusion will be assessed in 4-weekly categories (i.e. 4 weeks, 8 weeks, 12 weeks, ..., 104 weeks).

The time to discontinuation of IP is the same as the duration of exposure.

3.6 Safety variables

The following safety data will be collected: vital signs, physical examination, 12-lead ECG, haematology, clinical chemistry, urinalysis, C-SSRS (up to Week 52), PHQ-8 (up to Week 52), SLEDAI-2K based Flare Assessment Instrument, tuberculosis questionnaire, assessment of Cushingoid features, assessment of cardiovascular risk (fasting lipid profile) and reported AEs (including AESIs).

Any overdose report information collected will be listed only.

Change from baseline to each post-treatment time point where scheduled assessments were made will be calculated for relevant measurements.

If not stated otherwise, on-treatment values are defined as values with an assessment date after the first administration of IP and on or before the subject's Week 104 visit (Week 52 for C-SSRS and PHQ-8), or last visit if they withdraw early from the study.

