3.9 Discontinuation of investigational product

3.9.1 Criteria for discontinuation of investigational product due to worsening LN or SLE (at any time)

Blinded IP will be discontinued in subjects who meet pre-defined criteria for worsening LN or SLE. Subjects may receive rescue treatment as clinically indicated. Subjects who had their IP discontinued will be followed according to the study schedule. These subjects will be followed until Week 52 (or for a minimum of 12 weeks after last dose of IP for subjects for whom IP was discontinued within 12 weeks prior to Week 52). If discontinuation occurs during the second year extension period, subjects will be followed until Week 104 (or for a minimum of 12 weeks after last dose of IP for subjects for whom IP was discontinued within 12 weeks prior to Week 104).

- >30% decrease in eGFR compared to baseline due to LN and eGFR <60 mL/min/1.73 m² (on two independent samples) or
- Increase in renal or extra-renal lupus activity requiring prohibited systemic immunosuppressive treatment (eg, cyclophosphamide, rituximab, belimumab)
- Receipt of >1 methylprednisolone pulse after the day of randomisation
- Receipt of any methylprednisolone pulse after Week 8
- The IP will be discontinued if MMF is discontinued and another immunosuppressant is initiated

3.9.2 Criteria for discontinuation of investigational product for worsening of LN or SLE at Week 12 and Week 24

- eGFR <75% of baseline and <60 mL/min/1.73 m² (on two independent samples) or
- Nephrotic range UPCR (confirmed by a second measurement at least two weeks after the first measurement):
 - Subjects with 24-hour UPCR ≤3 mg/mg at baseline will be withdrawn if 24-hour UPCR increases by >50% from baseline to >3.5 mg/mg

- Subjects with 24-hour UPCR >3 mg/mg at baseline will be withdrawn if 24-hour UPCR at Week 24 >3.5 mg/mg and there is $<60\%$ improvement from baseline or
- Inability to adhere to corticosteroids requirements:
 - Inability to reduce OCS to ≤ 15 mg/day prednisone-equivalent at Week 12
 - Inability to reduce OCS to <15 mg/day by Week 24

Subjects who exceed the maximum daily OCS dose at the Week 12 or Week 24 visits may continue to receive IP if the current dose is part of a temporary increase in OCS dose (eg, protocol-allowed burst and taper). Subjects who cannot be returned to their pre-increase dose within 14 days from the start of the increase will have their IP discontinued at the next visit.

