3.6.1 Adverse events

Adverse events experienced by the subjects will be collected throughout the entire study, including the second year extension period, and will be coded using the latest version of MedDRA.

Adverse event data will be categorised according to their onset date into the following study periods:

- AEs occurring during screening:
An AE during screening is defined as an AE with a date of onset \geq date of the screening visit and date and time of onset $<$ date and time of the first dose of IP.
AEs occurring during screening will only be listed.
- AEs occurring during treatment:
An AE during treatment is defined as an AE with a date and time of onset \geq date and time of first dose of IP and \leq date of last dose of IP + 28 days.
- AEs occurring during follow-up:
An AE during follow-up is defined as an AE with a date of onset $>$ date of last dose of IP + 28 days and \leq date of last dose of IP + 84 days.
- AEs occurring after follow-up:
An AE after follow-up is defined as an AE with a date of onset $>$ date of last dose of IP + 84 days.
AEs occurring after follow-up will only be listed.

If an AE has a missing onset date, then unless the stop date of the AE indicates otherwise, this will be considered as an AE during treatment. Similarly, if an AE has a partial onset date, then unless the partial onset date or the stop date indicates otherwise, this will be considered an AE during treatment.

Adverse events with missing intensity will be assumed to be severe. Events with missing relationship to study medication per the investigator will be assumed to be related. If no information about seriousness is available, the AE will be considered serious.

An acute AE is defined as an AE with a date of onset on any day of administration of IP and a time of onset on or after the start of administration of IP or a date of onset occurring on the subsequent day. If an AE has a missing onset date, then unless the stop date of the AE indicates otherwise, this will be considered as an acute AE. Similarly, if an AE has a partial onset date, then unless the partial onset date or the stop date indicates otherwise, this will be considered acute AE.

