3.6.2 Laboratory variables

Parameters of haematology, clinical chemistry, urinalysis (outlined in Table 4, Section 5.4 of the clinical study protocol) and of fasting lipid profile (high density lipoprotein cholesterol, low density lipoprotein cholesterol, and triglycerides) will be examined.

Laboratory data will be reported in SI units. Changes from baseline in haematology, clinical chemistry and lipid profile variables will be calculated.

Absolute values will be compared to the reference range as given in [Appendix F](#) and classified as low (below range), normal (within range or on limits) or high (above range). All values (absolute and change) falling outside the reference ranges will be flagged.

Treatment emergent laboratory/vital signs changes (TELVC) will be defined for on-treatment values according to the reference ranges given in [Appendix F](#).

Urinalysis data that is continuous will be reported and summarised as for haematology and clinical chemistry data. Categorical urinalysis data will be categorised as negative (0), trace (trace), or positive (+, ++, +++, or >+++) at each time-point. Treatment-emergent changes will also be assessed. Treatment-emergent changes of urinalysis data are defined as

- Negative/+ at baseline to ++, +++, ++++ at any on-treatment value OR
- Increase of from baseline of at least ++ at any on-treatment value.

For the liver function tests: aspartate transaminase (AST), alanine transaminase (ALT), alkaline phosphatase (ALP), gamma glutamyl transferase (GGT) and total bilirubin, the multiple of the upper limit of the normal (ULN) range (see [Appendix F](#)) will be calculated for each data point as follows:

Multiple=Value/ULN (i.e. if the ALT value was 72 IU/L (ULN = 36) then the multiple would be 2)

Subjects meeting any of the following biochemical criteria for Hy's law (potential Hy's Law) at any point during the study will be flagged:

- $AST \geq 3x \text{ ULN}$
- $ALT \geq 3x \text{ ULN}$
- Total bilirubin $\geq 2x \text{ ULN}$

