3.6.6 Vital signs

Vital signs will be obtained at each visit and measured several times around each infusion of IP as follows:

- Subjects will be monitored during the administration of the IP and for at least two hours after the first 4 infusions (Weeks 0, 4, 8, and 12). If there are no safety concerns, for subsequent infusions subjects will be monitored during administration of the IP and for a minimum of one hour after completion of the IV infusion thereafter (Week 16 to Week 100).
- Vital signs in a sitting position will be taken:

- Shortly before the infusion (up to 20 minutes before the beginning of the infusion)
- Every 15±5 minutes during infusion
- Immediately after completion of administration of IP, including post-dose saline flush (within 20 minutes after completion of the post-dose saline flush)
- Every 30±5 minutes after completion of IP administration (not including saline flush) for at least 2 hours after the first 3 doses (Week 0 to Week 8) of IP are administered, and for at least 1 hour, thereafter (Week 12 to 100)

Vital signs may also be taken more frequently if the investigator judges this to be appropriate.

The following vital signs will be examined:

- Pulse (beats per minute)
- Systolic blood pressure (mmHg)
- Diastolic blood pressure (mmHg)
- Respiration rate (breaths per minute)
- Body temperature (°C)

Changes from baseline will be calculated.

Where applicable, absolute values will be compared to the reference ranges given in [Appendix G](#) and classified as low (below range), normal (within range or on limits) or high (above range). All values (absolute and change) falling outside the reference ranges will be flagged.

On-treatment values will be classified as TELVC according to reference ranges given in [Appendix G](#).

Weight (kg) and BMI (kg/m²) will be measured at all study visits and examined using the difference in mean change from baseline longitudinally over time. BMI will be calculated at all visits using the associated visit weight measurement and the height measured at screening.

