4.2.6.2 Laboratory variables

Observed values and changes from baseline of laboratory data for haematology, clinical chemistry and fasting lipid profile will be summarised by visit. The summary statistics presented will be minimum, 1st quartile, median, 3rd quartile, maximum, mean, and SD.

Shift plots (scatter plots) for each of the parameters presenting baseline values versus minimum post-baseline values and maximum post-baseline values, respectively, will be provided. A diagonal line indicating no change and horizontal and vertical reference lines indicating the limits of the reference ranges will also be displayed on the shift plots.

If any laboratory variables show any unusual features (high or low values or a general shift in the data points) at specific visits, then shift plots of these data may also be produced. This will be discussed and agreed upon during the BDR meeting.

For each laboratory parameter with available criteria, the number and percentage of subjects with TELVC values will be summarised by visit. Additionally, the number and percentage of subjects with at least one TELVC value will be presented.

The number and percentage of subjects with laboratory values below, within or above the corresponding normal range will be presented by visit. Urinalysis will be summarised as shift tables from baseline to the last on-treatment value for each parameter. Furthermore, the number and percentage of subjects with treatment-emergent changes will be summarised by parameter. In addition, observed values and change from baseline and pre-specified categories will be summarised by visit for any continuous variables.

In order to identify potential Hy's Law cases, the number and percentage of subjects in categories based on multiples of ULN for maximum on-treatment ALT and AST by maximum total bilirubin will be presented in a table. The table will include the following categories: < and $\geq 2xULN$ for total bilirubin and < $3xULN$, $\geq 3 - < 5xULN$, $\geq 5 - < 10xULN$ and $\geq 10xULN$ for ALT/AST.

Individual subject data will be presented for all subjects who meet the criteria for potential Hy's law. The relevant laboratory parameters (ALT, AST, total bilirubin and ALP) will be tabulated showing all visits for these subjects. Subjects with elevated ALT or AST (ALT or AST $\geq 3 \times \text{ULN}$) and elevated total bilirubin ($\geq 2 \times \text{ULN}$) at any time during the study (not necessarily at the same time) will be included.

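### On-treatment laboratory, vital-sign and urinalysis values run to Week 104 or the last visit whatever the date of the last dose, while adverse events stop at last dose plus 28 days

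*SAP*

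**What the plan says.** SAP Section 3.6 gives a default that applies unless another section overrides it. It fixes the start of the window with these words: "on-treatment values are defined as values with an assessment date after the first administration of IP". The end of the window is tied to a visit and not to dosing, since a value still counts when it was taken "on or before the subject's Week 104 visit (Week 52 for C-SSRS and PHQ-8), or last visit if they withdraw early from the study". The early exit named there is from the study, not from IP.

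Several outputs are built on this default:

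- Laboratory values (SAP 3.6.2): "Treatment emergent laboratory/vital signs changes (TELVC) will be defined for on-treatment values according to the reference ranges given in" Appendix F.
- Categorical urinalysis (SAP 3.6.2): a change is treatment-emergent if it occurs "at any on-treatment value".
- Vital signs (SAP 3.6.6): "On-treatment values will be classified as TELVC according to reference ranges given in" Appendix G.
- Urinalysis shifts (SAP 4.2.6.2): "Urinalysis will be summarised as shift tables from baseline to the last on-treatment value for each parameter".
- SAP 4.2.6.2 also cross-tabulates peak on-treatment ALT and AST against peak bilirubin, and SAP 4.2.6.3 has an ECG shift table to the last on-treatment tracing.

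Other safety outputs use a different rule. SAP 3.6.1 begins "An AE during treatment is defined as an AE with a date and time of onset" at or after the first dose, and closes the period 28 days after the last dose. Exposure (SAP 3.5.5), the adverse event rate denominator (SAP 3.6.1) and on-treatment extra-renal flares (SAP 4.2.6.4) end at the same point.

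On follow-up after IP stops, Protocol 3.9.1 keeps subjects on the visit schedule to Week 52 or Week 104 and adds: "Subjects may receive rescue treatment as clinically indicated". Protocol 4.2.2 lists chemistry, haematology, urinalysis and vital signs among the assessments to be completed in these subjects.

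**The concern.** A table headed treatment-emergent should describe subjects while they are exposed, or shortly after. Under SAP 3.6 it also describes subjects who are off IP and possibly on rescue immunosuppression. The row counting subjects with at least one treatment-emergent value is the most exposed, because one late value is enough to put a subject in it.

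The laboratory tables matter more here than in many trials. Under Protocol 6.5.6, deterioration in a protocol-mandated laboratory value or vital sign becomes an adverse event only if it is serious or is the reason for stopping IP; associated symptoms are reported separately. Silent, non-serious cytopenias and liver changes will therefore be seen mainly in the laboratory tables, and the correctly windowed adverse event tables cannot stand in for them.

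The SAP already accepts the principle elsewhere. Its version 4.0 entry gives rescue after IP discontinuation as the reason for changing the estimand of the continuous endpoints, and SAP 4.2.5.2 splits disallowed medications into on and off IP.

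**Working it through.** The plan states no figure to reproduce, so the check compares the two windows.

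**Inputs.** Study day = 7 × week + 1 (SAP 4.1.1). Laboratory visits are 4-weekly (Protocol Tables 2 and 4). Follow-up after stopping IP runs to Week 52 in year 1 and Week 104 in year 2 (Protocol 3.9.1).

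**Formulas.** Adverse event window end = day of last dose + 28. SAP 3.6 window end = Day 365 (Week 52) or Day 729 (Week 104). Excess = the difference. Visits are nominal and post-baseline.

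| Last dose | Dose day | Last dose + 28 | SAP 3.6 end | Excess days | Visits under 3.6 | Visits by last dose + 28 |
|---|---|---|---|---|---|---|
| Week 0 | 1 | 29 | 365 | 336 | 13 | 1 |
| Week 8 | 57 | 85 | 365 | 280 | 13 | 3 |
| Week 20 | 141 | 169 | 365 | 196 | 13 | 6 |
| Week 48 | 337 | 365 | 365 | 0 | 13 | 13 |
| Week 52 | 365 | 393 | 729 | 336 | 26 | 14 |
| Week 56 | 393 | 421 | 729 | 308 | 26 | 15 |
| Week 100 | 701 | 729 | 729 | 0 | 26 | 26 |

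The windows coincide for subjects who complete dosing and diverge only for those who stop early. For a subject last dosed at Week 8, 13 − 3 = 10 of the 13 on-treatment visits fall outside the adverse event window.

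SAP 3.6 does not settle whether Weeks 56 and 60 count for a subject dosed through Week 48 who does not enter year 2. If they do, a further 421 − 365 = 56 days and 2 visits enter.

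**Is there an override?**

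- The C-SSRS composites (SAP 3.6.9) and flares (SAP 4.2.6.4) state their own periods. The laboratory, vital-sign and ECG sections do not.
- SAP 4.1.3 cuts continuous endpoints at IP discontinuation, which SAP 4.2.1 presents as the estimand for those endpoints. Counts of subjects with a treatment-emergent value are not continuous endpoints. If the rule did reach mean laboratory changes, the means and the counts would use different windows.
- Appendices F and G were not available for this check; the SAP cites them only for reference ranges.

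**The case against.** The case for leaving the rule alone has several parts.

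- **These are descriptive tables.** No hypothesis test is affected. Treatment-emergent counts are shown by visit, so timing is visible. This is true, but by-visit counts do not separate subjects on IP from those off it, and the at-least-one row loses timing altogether.
- **Some data types are barely touched.** ECG has only a shift table, with tracings at screening, Week 52 and Week 104, and ECG is not on the minimum list after IP stops. A reader might infer treatment-emergent ECG tables; there are none. Vital signs are summarised around infusions, so a subject off IP can add only visit readings. Both limits stand.
- **The direction of bias is not known.** A reader might infer that rescued placebo subjects raise the placebo rate and mask a drug effect. Stopping is tied to worsening disease, so this is possible, but the documents give no stopping or rescue rates by arm, and the reverse pattern would inflate the anifrolumab rate. MMF, which Protocol 6.11.3 links to neutropenia, may also continue after IP stops, so an off-IP abnormality need not reflect rescue.
- **Double classification is narrow.** After a last dose at Week 8 (Day 57), an adverse event at Week 36 (Day 253, 196 days later) lies beyond last dose + 84 days and is only listed, while a laboratory value that day can be treatment-emergent. Under Protocol 6.5.6 this arises mainly for serious or symptomatic cases.
- **Not every subject who stops IP contributes.** Protocol 4.2.2 allows unwilling subjects to finish early or move to telephone contact.
- **A bare cut-off at last dose + 28 days would lose good data.** That falls on Day 365 or Day 729, and the Week 52 and Week 104 visits may be up to 7 days late. This stands, and the fix must allow for it.

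**Conclusion.** The inconsistency is real. The SAP holds two meanings of on-treatment, and the one applied to laboratory values, urinalysis and vital signs has no link to exposure. For early stoppers followed to Week 52 or Week 104, the examples above put 196 to 336 days beyond last dose + 28 days into the on-treatment period. The effect on the ECG shift table is minor.

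These figures assume nominal visit days and full follow-up after stopping. They measure how far the window overruns in one subject, not the change in any event rate. Without a stopping rate in the documents, neither the share of affected data nor a between-arm bias can be calculated. The documents therefore do not support a claim that a safety signal is masked, nor a claim that the wide window is conservative.

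The rule should be corrected because it mislabels data that are a main source for silent laboratory abnormalities. It does not affect the primary or secondary efficacy tests.

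**What to change.** In SAP 3.6, define on-treatment safety values as those after the first dose and up to last dose + 28 days, plus the 7-day visit window. For a last dose on Day 57 this ends on Day 57 + 28 + 7 = 92. It admits no extra scheduled visit, because Week 16 cannot be in window before Day 113 − 7 = 106.

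Add that a subject dosed in the Week 48 or Week 100 window keeps the Week 52 or Week 104 value, in line with the Week 48 rule in SAP 4.1.3 and 4.2.1. The 7 days alone do not guarantee this: a Week 48 dose 7 days early (Day 330) and a Week 52 visit 7 days late (Day 372) are 42 days apart, against 35 allowed.

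Tabulate later values separately as off-treatment or follow-up, and state where Weeks 56 and 60 belong for subjects who do not enter year 2. Keep the potential Hy's Law listing that covers any time in the study and, if wanted, a whole-study table as a supplement.

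The cost is SAP wording, programming and some extra tables; no new data are needed. Late values leave the on-treatment summaries but remain reported, and the laboratory window will differ from the adverse event window by the stated allowance.
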